8.1. First level

ASRS: All Subjects randomized set.

ASTS: All Subjects treated set. All subjects in ASRS, who have received at least one administration of IMP.

FAS: Full Analysis set. All subjects in the ASTS, who have a baseline assessment and at least one assessment of the primary outcome (RBANS) after first administration of IMP. If an IST has a key outcome different from the RBANS, the ISA-SAP may make use of a definition covering at least one assessment of the primary outcome (RBANS) or the key outcome, after first administration of IMP.

8.2. Second level

IST controls: All subjects in all treatment arms in the IST.

Concurrent controls: All subjects in all treatment arms in the IST supplemented with control subjects from other ISTs, defined as follows: The present IST has a First Subject First Visit (FSFV) and Last Subject First Visit (LSFV), and a specified intended study duration. The dates refer to the baseline visit. The placebo subjects contributing from other ISTs are all subjects with a Visit 2 (baseline) date between the dates of the first subject first visit (FSFV) and the last subject first visit (LSFV) in the focus IST(both

 EPAD - 115736	D2.11 Master Statistical Analysis Plan for the EPAD Platform Proof-of-Concept Trial		
	WP2. Statistical/Methodology Engine Room	Version: v2.0 – Final	
	Author(s): [name], [name], [name]	Security: PU	21/36

dates included). Here FSFV and LSFV refer to the baseline visits. Only data from research participants from the strata included in the focus IST are shared. Individual data will be used until the minimum of the study durations of the relevant study and the other study. So, if the actual IST runs over 2 years and the other study over 4 years, only data up to 2 years will be shared. On the other side if the actual IST runs over 4 years and the other study over 2 years, still only data up to 2 years will be shared as further data are not available.

All controls: Defined similar to the concurrent controls, but without the condition of start in PoC between FSFV (inclusive) and LSFV (inclusive). Before unblinding, a cut-off will need to be set regarding the last enrolment day to include. The cut-off date should allow for including data from the Month 6 visit. Research participants who cannot have experienced their Month 6 visit are not included.

8.3. Third level

Without qualifier: Subjects as restricted by the first and second level.

With qualifier “controls-only”. Subjects as restricted by the first and second level and included in the control arms of the studies.

8.4. General

Additional analysis sets can be defined in the ISA. The ISA will also outline a strategy with respect to estimands as the intercurrent events and strategy may depend on the actual intervention considered. For the primary analysis, we may need to consider an appropriate estimand.

The interim analysis calculations are based on the Missing At Random assumption, corresponding to a hypothetical estimand.

No calculations will involve unblinded data from active treatments from several ISTs unless agreed by all owners of compounds involved in the calculation.

The patients and data will be classified into the analysis set(s) during a classification meeting according to the definitions above after the study database has been released, but before the blind has been broken.

The primary endpoint includes data transferred from the LCS study, covering the full period from enrolment in the LCS until enrolment in the POC.

9. Descriptive statistics

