4.4. Safety objectives(s)

The safety of an intervention will be monitored throughout the trial.

5. Study Design

This is a multi-centre, multi-national, double-blind, randomized, placebo-controlled, adaptive, perpetual platform clinical trial to investigate the efficacy and safety of multiple drugs simultaneously or sequentially.

There will be multiple interventions, where the research participants on an intervention and its specific blinded placebo are labelled as the intervention specific trial population. Intervention specific trial populations may start at different time points in the course of the trial. Therefore, the double-blind will be maintained within an intervention specific trial population between the different arms in that cohort. Research participants will not be blinded to which intervention specific trial they participate in. For an intervention specific trial, the number of intervention arms versus placebo will be defined in the Intervention Specific Appendix. The randomization ratio within each intervention specific trial is 3:1 (total active arms: placebo). Each intervention arm within an intervention specific trial is labelled as a subarm.

This adaptive platform design will utilise common control research participants from multiple intervention specific trials and common minimum success and futility criteria evaluated at the interim analyses. The ISA may describe further adaptive features, referring to the IST, such as changes in allocation ratios for the active arms, when there are multiple active arms

Research participants who have been enrolled in the LCS for the below minimum time points will be invited to participate in the PoC trials (note that the criteria referring to CSF may have been assessed at an earlier time point):

1. For prodromal research participants they have completed Visit 2/Month 6 procedures in the EPAD LCS.
2. For preclinical research participants they have completed Visit 3/Month 12 procedures in the EPAD LCS.

The allocation procedure is illustrated in Figure 1. Research participants who provide consent at the transition visit will have an eligibility check done and then be randomly allocated to one of the ongoing Intervention-specific Trials in the EPAD PoC trial for which they are eligible. The participant will be informed of this allocation and provided with written information specific to the IST, then subject to consent they will begin screening procedures for the IST.

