 EPAD - 115736	D2.11 Master Statistical Analysis Plan for the EPAD Platform Proof-of-Concept Trial		
	WP2. Statistical/Methodology Engine Room	Version: v2.0 – Final	
	Author(s): [name], [name], [name]	Security: PU	13/36

If eligibility criteria are fulfilled, they will then be randomized on a 3:1 ratio to the intervention active arm or placebo. If there are subarms for an intervention (doses, frequency) then a further randomization would determine the subarm.

In case of a screening failure, participants can be re-randomized as follows:

- Participants who fail to meet eligibility criteria for the Master Protocol will have the possibility to continue to be followed in the LCS until they are eligible for the PoC Platform Clinical Trial Master Protocol
- Participants who fail to meet eligibility criteria during the screening of an intervention will have the possibility to be re-assigned to another intervention for which they are eligible (except see below)
- Participants assigned to an intervention but who withdraw consent for personal reasons (eg, inconvenience of the intervention, mode of administration, etc.) will not be re-assigned to another intervention for 12 months. If a second withdrawal of consent after randomization to the Master Protocol occurs, the subject will be permanently discontinued from the EPAD studies including LCS.

The duration of treatment for each intervention, the follow-up period and the end of the intervention-specific trial will be described in the Intervention Specific Appendix. On the participant level, the trial duration can be up to four years.

At minimum, on-site visits will occur every 3 months during the first year and every 6 months for the remaining years of the trial.

The primary and secondary clinical outcomes will be assessed for all interventions every 6 months. More frequent assessments are discouraged because of the potential learning effects, which could lead to discrepancies between different assessments and therefore a potential bias in the results.

Evolution analyses will take place quarterly within the platform trial. At each of these evolution analyses a set of possible evolutions or adaptations that an intervention is eligible for will be checked.

[figure not shown]

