This section covers only the final analysis. The interim analyses are similar with additional description in Section 18.1. This section is not completely final. More work is needed regarding the details of the approach. Besides, the assumptions need justification.

The primary efficacy analyses are based on a Bayesian cognitive progression model (BCPM). This cognitive progression model incorporates the following aspects:

- Repeated measures for the cognitive endpoint over the recurring 6-month visit schedule, including pre- and post-intervention
- Patient-level random effect
- Proportional treatment effect for slowing of disease progression rate. If there are several active treatment arms, the ISA will describe how this will be modelled.

Let a cognitive endpoint at visit j for research participant i be labelled Y_{ij} , for $j = \dots, -1, 0, 1, 2, \dots$. The reference to negative visits corresponds to cognitive endpoint values from the LCS study, pre-intervention. The Y_{i0} observation corresponds to the baseline visit at the time of the start of intervention. Visits $j=1,2,3$, refer to the post baseline, on treatment visits (each 6-months separated). Within a specific subgroup, the cognitive progression model is

 EPAD - 115736	D2.11 Master Statistical Analysis Plan for the EPAD Platform Proof-of-Concept Trial		
	WP2. Statistical/Methodology Engine Room		Version: v2.0 – Final
	Author(s): [name], [name], [name]		Security: PU

$$Y_{ij} = \begin{cases} \gamma_i + \sum_{v=j}^{-1} \alpha_v + \epsilon_{ij} & j = \dots, -2, -1 \\ \gamma_i + \epsilon_{ij} & j = 0 \\ \gamma_i + \exp(\theta_{t_i}) \sum_{v=1}^j \alpha_v + \epsilon_{ij} & j = 1, 2, 3 \dots \end{cases}$$

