The γ_i , $i=1, \dots, k$, parameters are the random effects specific to a research participant. These random effects represent the mean cognitive total score at the time of treatment (randomization). The α_j parameters represent the change in the mean cognitive score from one visit to the next. The α_j , for $j=0, 1, 2, 3$, are restricted to be negative (decline), representing the mean change from visit $j-1$ to j , restricted to be, on average, negative. For research participant i , the treatment arm is labelled t_i . The cognitive progression rate ratio (CPRR) for treatment T is the parameter $\exp(\theta_T)$. For a control, or placebo treatment, the CPRR is assumed to be 1 ($\theta_T = 0$). Thus, the CPRR parameter for a generic intervention T represents the multiplicative change to the mean decline of a research participant on a control or placebo treatment. If the CPRR is less than 1 then the rate of decline for an intervention T is slower than for a control treatment. The value of the CPRR represents the proportional slowing of the disease. A value of CPRR = 0.75 corresponds to a 25% slowing in the rate of decline and a value of 0.25 represents a 75% slowing in the rate of decline. The errors for the individual observations are modelled as independent normal distributions with a standard deviation of σ . Within each defined subgroup (strata), $g=1, 2, 3, 4$, corresponding to the cognitive status and ApoE4 status ($g=1$ is (+,+), $g=2$ is (+,-), $g=3$ is (-,+), and $g=4$ is (-,+)), a separate set of α 's and σ are modelled (α_g and σ_g). In the primary analysis, the same CPRR is assumed across these subgroups.

The prior distributions for the RBANS total score variable, within each subgroup are presented in this section. Alternative endpoints analysed using this BCPM will have these prior parameters specified separately. The research participant level random effects are modelled as

$$\gamma_i \sim N(\mu, 12^2), i=1, \dots, k$$

with hyper-priors by sub-group:

$$\mu \sim N(\mu_{sg}, \tau_{sg}^2)$$

where for clinically negative: $\mu_{sg} = 100$, $\tau_{sg} = 2.25$ and for clinically positive: $\mu_{sg} = 88.75$, $\tau_{sg} = 3.75$ (the parameters don't change for ApoE4 status)

 EPAD - 115736	D2.11 Master Statistical Analysis Plan for the EPAD Platform Proof-of-Concept Trial		
	WP2. Statistical/Methodology Engine Room	Version: v2.0 – Final	
	Author(s): [name], [name], [name]	Security: PU	25/36

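### The primary model uses every LCS RBANS score with no first-test term, so CPRR can be biased if LCS duration differs between an IST and its borrowed placebo

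*Combined protocol and SAP*

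**What the plan says.** Section 8.4 states that the primary endpoint includes data transferred from the LCS, "covering the full period from enrolment in the LCS until enrolment in the POC". No test is left out. Section 14 describes the model as "Repeated measures for the cognitive endpoint over the recurring 6-month visit schedule, including pre- and post-intervention" and explains the index: "The reference to negative visits corresponds to cognitive endpoint values from the LCS study, pre-intervention". Each participant has a random effect (gamma) for the level at the start of treatment, and post-baseline change is measured from it. Visit effects (alpha) are separate for four strata, "corresponding to the cognitive status and ApoE4 status". CPRR multiplies only the post-baseline changes.

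Section 5 sets minimum LCS times and no maximum: "For prodromal research participants they have completed Visit 2/Month 6 procedures in the EPAD LCS", and "For preclinical research participants they have completed Visit 3/Month 12 procedures in the EPAD LCS". On repeated testing it says: "More frequent assessments are discouraged because of the potential learning effects". It names bias as the reason but gives no size.

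Section 18.1 bases graduation and futility on the Section 14 analysis. On the primary control set the SAP disagrees with itself: Section 8 names FAS-concurrent controls, and Section 14 item 1 names FAS-All controls, which has no enrolment window. Section 14 item 3 is an analysis from baseline onward, without LCS data, as one of the additional analyses.

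**The concern.** Take two participants in the same stratum. One enters the PoC after two LCS tests, so the first LCS test sits at j = -2. The other enters after four, so the first sits at j = -4 and j = -2 is a third test. One alpha for j = -2 has to serve both. If the first score is low for want of practice, the fitted mean at j = -2 lies between the two. The short-LCS participant's score then falls below the fit and pulls that participant's gamma down, so later decline from gamma looks smaller. The long-LCS participant is affected the other way at that visit.

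Randomisation within an IST balances LCS duration between its own arms. It does not balance duration between the IST and placebo from other ISTs. If the mix differs there, part of the first-test effect is read as a treatment effect in the analysis that decides graduation and futility, where the threshold is a CPRR of 0.90.

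**Working it through.** The SAP states no sample size, power or bias figure for this point (Section 19 defers them to the ISA), so there is nothing to reproduce. I computed the value to which the Section 14 model would converge.

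**Inputs from the SAP**
- Between-participant SD 12 (Section 14).
- Residual variance 25, so SD 5 (Annex I starting value).
- Placebo change at 6, 12, 18 and 24 months: -2, -3, -4, -5 (slower) and -5, -8, -11, -14 (steeper). These are Annex I starting values, not design assumptions.
- 3:1 allocation within an IST (Section 5).

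**Assumptions**
- 150 active, 50 own placebo, 100 borrowed placebo.
- Short LCS = 2 tests, long LCS = 4 tests.
- Only the first LCS score is lowered, by 2 or 4 points.
- Pre-baseline visit means are free.

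**Method.** For each group g (arm by LCS length) with n_g participants and expected profile m_g, minimise over CPRR c and visit means b:

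sum over g of n_g (m_g - X_g(c) b)' V_g^-1 (m_g - X_g(c) b), with V_g = 144 J + 25 I (J all ones, I identity).

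**Results for an inert drug (true CPRR 1)**

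| Short-LCS share, focus IST v borrowed | Declines | Gain 2 | Gain 4 |
|---|---|---|---|
| 50% v 50% | either | 1.000 | 1.000 |
| 55% v 45% | slower | 0.991 | 0.983 |
| 70% v 30% | slower | 0.965 | 0.931 |
| 70% v 30% | steeper | 0.987 | 0.975 |
| 30% v 70% | slower | 1.035 | 1.072 |
| 30% v 70% | steeper | 1.012 | 1.025 |

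With both strata fitted under one CPRR, as Section 14 specifies, the 70% v 30% result is 0.985 to 0.970 and the reverse mix gives 1.015 to 1.030. Residual SD 9 changes the slower 70% v 30% row only to 0.968 and 0.937. With the slower declines, a true 0.90 becomes 0.867 to 0.834 (70% v 30%), and a true 0.75 becomes 0.781 to 0.813 (30% v 70%).

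**Effect on one look at the success rule** (slower declines, normal approximation, prior SD 0.25 on log-CPRR, SE 0.106)
- Weight on the data: 0.0625 / (0.0625 + 0.01124) = 0.848.
- Posterior SD: sqrt(0.848 x 0.01124) = 0.098.
- Success needs a posterior mean below ln 0.90 - 1.036 x 0.098 = -0.207, so an estimate below -0.207 / 0.848 = -0.244 (CPRR about 0.78).
- Inert drug: z = -0.244 / 0.106 = -2.30, probability 1.1%.
- Shifted to 0.965: z = (-0.244 + 0.036) / 0.106 = -1.96, probability 2.5%.
- Shifted to 0.931: z = (-0.244 + 0.072) / 0.106 = -1.62, probability 5.2%.

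**Remedies in the same setting.** A first-administration parameter outside the multiplier, or dropping the first LCS score, returns CPRR to the true value. With equal mixes and the slower declines, the SE of CPRR is 0.106 with all data, 0.106 with the parameter, 0.113 with the first score dropped, and 0.144 from baseline onward only.

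**The case against.** The strongest reply is that the harm needs an imbalance the documents do not show. Consenting participants are allocated at random among the ongoing ISTs for which they are eligible, and concurrent controls must have their baseline within the focus IST's enrolment window. Together these tend to balance LCS duration, leaving IST-specific eligibility, re-assignment after screening failure and partial overlap of ISTs. This stands. Imbalance is much more plausible under FAS-All controls, where placebo from earlier or later ISTs is pooled without a window. Which case applies turns on the unresolved conflict between Sections 8 and 14.

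It also stands that the SAP gives no size for learning, does not say that it persists at six-month intervals, and does not say that the first LCS RBANS is a participant's first exposure to the test. Section 14 describes itself as not fully final.

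The planned additional analyses help only in part. Item 3 and the IST-controls analysis could reveal the problem but do not drive graduation. The poolability check covers concurrent controls only, states no consequence, and on its face uses the same indexing. The calendar-time term in item 5 is constant over a participant's visits, so it cannot absorb a low first score. The Annex I code starts at baseline and does not show how LCS scores are handled.

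**Conclusion.** The gap in the model is in the text: all LCS scores enter, they are indexed backward, nothing represents test number, and durations can vary within a stratum. Whether it biases CPRR is conditional on two things together: a first-to-second-test gain, and a duration mix that differs between the focus IST and borrowed placebo. Under the stated assumptions the shift for an inert drug runs from under 0.01 (55% v 45%, gain 2, slower declines) to about 0.07 (70% v 30%, gain 4, slower declines). With the steeper declines the 70% v 30% shift is about one third as large.

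A reader might infer more, and three such readings are not supported:
- That CPRR is biased as the plan stands. The documents contain no LCS durations by IST or control source.
- That the bias has a known direction. Borrowed placebo with longer LCS time lowers CPRR, and with shorter time raises it.
- That unequal LCS durations do harm by themselves. With equal mixes and free pre-baseline means they do not.

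One limit applies to all these figures. The printed prior makes every alpha negative. If the pre-baseline effects are really sign-restricted, neither the sizes above nor the no-bias result for equal mixes need carry over.

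**What to change.** In Section 14, for the final and interim models, add one first-LCS-administration parameter per stratum that is neither multiplied by CPRR nor restricted in sign. In the setting above this costs essentially no precision (SE 0.106 either way). The alternative is to exclude each participant's first LCS RBANS, which widens the SE by about 6.5% (0.106 to 0.113). Section 8.4 should be worded to match.

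Keep item 3 as the sensitivity analysis. Either fix removes the bias fully only if learning is confined to the first test. If the second test keeps half the deficit, dropping the first still leaves 0.976 to 0.953 (inert drug, 70% v 30%, slower declines). Making item 3 primary would be dearer: 0.144 / 0.106 = 1.36, an SE about 36% wider.

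Report the number of LCS tests by stratum for active, own placebo and borrowed placebo, and reconcile Sections 8 and 14 on the primary control set. The cost is a few lines of specification, one more parameter per stratum and one table.

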9.1. Final report

Unless otherwise specified, summary statistics (n, arithmetic mean, standard deviation [SD], median, lower and upper quartiles, minimum and maximum values) will be presented for continuous variables, and counts and, if relevant, percentages will be presented for categorical variables.

 EPAD - 115736	D2.11 Master Statistical Analysis Plan for the EPAD Platform Proof-of-Concept Trial		
	WP2. Statistical/Methodology Engine Room	Version: v2.0 – Final	
	Author(s): [name], [name], [name]	Security: PU	22/36

Unless otherwise specified, descriptive statistics will be given for the subpopulations corresponding to preclinical versus prodromal patients, positive versus negative Apolipoprotein E (ApoE4) genetic status and the four combinations thereof.

Unless otherwise specified, data listings will include site, treatment group, patient screening number, sex, age, race (when collected), and baseline weight. Listings will not include research participants from other IST's if their treatment status is still blinded in the relevant IST.

9.2. Interim report for DSMB

This section is not finalized.

10. Patient disposition

10.1. Final report

Patient disposition will be summarised by treatment group and include the number of patients who completed and the number of patients who withdrew from treatment, as well as the number of patients in each analysis set.

The number of patients who withdrew from treatment will be summarised by treatment group and primary reason for withdrawal (withdrawal of consent, concomitant medication, adverse event, loss to follow-up, IST stopped) as well as by treatment group and all reasons for withdrawal.

10.2. Interim report for IDMC

10.3. This section is not finalized Interim report for DSMB

This section is not finalized.

We will also need to include ongoing patients.

11. Demographics and baseline characteristics

Demographics (including sex, age, country, race(when collected)), other baseline characteristics (including height, weight, BMI, subgroup classification), and baseline efficacy variables (including RBANS, CDR status, CSF biomarker status) will be summarised by treatment group and per combination of subpopulation and treatment group (preclinical versus prodromal patients, positive versus negative Apolipoprotein E (ApoE4) genetic status and the four combinations thereof), as well as per combination of treatment group and analysis set.

12. Recent and concomitant medication

Recent and concomitant medication will be coded using the Medical Dictionary for Regulatory Activities (MedDRA) coding dictionary

 EPAD - 115736	D2.11 Master Statistical Analysis Plan for the EPAD Platform Proof-of-Concept Trial		
	WP2. Statistical/Methodology Engine Room	Version: v2.0 – Final	
	Author(s): [name], [name], [name]	Security: PU	23/36

Medications will be classified according to the start and stop time and summarized by anatomical therapeutic chemical (ATC) code, generic drug name, treatment group, and period (if different (treatment) periods are included in the study, specify by period):

- medication discontinued prior to first dose of IMP
- concomitant medication continued after first dose of IMP
- concomitant medication started at or after first dose of IMP

If concomitant medications are collected after withdrawal from treatment in studies with follow-up of withdrawn patients, present concomitant medication started after withdrawal from treatment separately:

- concomitant medication started after last dose of IMP

13. Exposure and compliance

Research participants are requested to bring back all remaining trial medication including empty package material with them when attending visits (might not be possible for injectable product). Treatment compliance will be calculated for each intervention cohort (details will be found in the ISA). Compliance will be verified by the on-site monitor authorized by the Sponsor.

Exposure will be calculated based on total daily dose over treatment duration in months/years. Details of any exposure assessments required for the trial drug will be reported in the ISA.

14. Efficacy

This section covers only the final analysis. The interim analyses are similar with additional description in Section 18.1. This section is not completely final. More work is needed regarding the details of the approach. Besides, the assumptions need justification.

The primary efficacy analyses are based on a Bayesian cognitive progression model (BCPM). This cognitive progression model incorporates the following aspects:

- Repeated measures for the cognitive endpoint over the recurring 6-month visit schedule, including pre- and post-intervention
- Patient-level random effect
- Proportional treatment effect for slowing of disease progression rate. If there are several active treatment arms, the ISA will describe how this will be modelled.

Let a cognitive endpoint at visit j for research participant i be labelled Y_{ij} , for $j = \dots, -1, 0, 1, 2, \dots$. The reference to negative visits corresponds to cognitive endpoint values from the LCS study, pre-intervention. The Y_{i0} observation corresponds to the baseline visit at the time of the start of intervention. Visits $j=1,2,3$, refer to the post baseline, on treatment visits (each 6-months separated). Within a specific subgroup, the cognitive progression model is

 EPAD - 115736	D2.11 Master Statistical Analysis Plan for the EPAD Platform Proof-of-Concept Trial		
	WP2. Statistical/Methodology Engine Room		Version: v2.0 – Final
	Author(s): [name], [name], [name]		Security: PU

$$Y_{ij} = \begin{cases} \gamma_i + \sum_{v=j}^{-1} \alpha_v + \epsilon_{ij} & j = \dots, -2, -1 \\ \gamma_i + \epsilon_{ij} & j = 0 \\ \gamma_i + \exp(\theta_{t_i}) \sum_{v=1}^j \alpha_v + \epsilon_{ij} & j = 1, 2, 3 \dots \end{cases}$$

The γ_i , $i=1, \dots, k$, parameters are the random effects specific to a research participant. These random effects represent the mean cognitive total score at the time of treatment (randomization). The α_j parameters represent the change in the mean cognitive score from one visit to the next. The α_j , for $j=0, 1, 2, 3$, are restricted to be negative (decline), representing the mean change from visit $j-1$ to j , restricted to be, on average, negative. For research participant i , the treatment arm is labelled t_i . The cognitive progression rate ratio (CPRR) for treatment T is the parameter $\exp(\theta_T)$. For a control, or placebo treatment, the CPRR is assumed to be 1 ($\theta_T = 0$). Thus, the CPRR parameter for a generic intervention T represents the multiplicative change to the mean decline of a research participant on a control or placebo treatment. If the CPRR is less than 1 then the rate of decline for an intervention T is slower than for a control treatment. The value of the CPRR represents the proportional slowing of the disease. A value of CPRR = 0.75 corresponds to a 25% slowing in the rate of decline and a value of 0.25 represents a 75% slowing in the rate of decline. The errors for the individual observations are modelled as independent normal distributions with a standard deviation of σ . Within each defined subgroup (strata), $g=1, 2, 3, 4$, corresponding to the cognitive status and ApoE4 status ($g=1$ is (+,+), $g=2$ is (+,-), $g=3$ is (-,+), and $g=4$ is (-,+)), a separate set of α 's and σ are modelled (α_g and σ_g). In the primary analysis, the same CPRR is assumed across these subgroups.

The prior distributions for the RBANS total score variable, within each subgroup are presented in this section. Alternative endpoints analysed using this BCPM will have these prior parameters specified separately. The research participant level random effects are modelled as

$$\gamma_i \sim N(\mu, 12^2), i=1, \dots, k$$

with hyper-priors by sub-group:

$$\mu \sim N(\mu_{sg}, \tau_{sg}^2)$$

where for clinically negative: $\mu_{sg} = 100$, $\tau_{sg} = 2.25$ and for clinically positive: $\mu_{sg} = 88.75$, $\tau_{sg} = 3.75$ (the parameters don't change for ApoE4 status)

 EPAD - 115736	D2.11 Master Statistical Analysis Plan for the EPAD Platform Proof-of-Concept Trial		
	WP2. Statistical/Methodology Engine Room	Version: v2.0 – Final	
	Author(s): [name], [name], [name]	Security: PU	25/36

The prior for the individual visit effects are modelled as:

$$-\alpha_v \sim IG(0.01, 1).$$

The prior for the variance component for the error term is

$$\sigma^2 \sim IG(81, 9).$$

The prior distribution for the log-CPRR is

$$\theta \sim N(0, 0.25^2)$$

The prior distribution of the treatment effect is centered on no treatment effect (0). A one-SD change in the prior effect is, $\exp(-0.25) = 0.78$, and a two-SD decline in the rate is $\exp(-0.5) = 0.61$. This prior was selected to allow the PoC data to shape the posterior distribution for the treatment effect, yet to provide a small amount of pessimism on the treatment effect.

For each intervention a separate instance of the model is run. The exact same model specification is used for each, but the model is run separately with each intervention and collection of placebos.

The primary analysis considers only observed observations and does not impute missing data.

For each run of this primary analysis model, the following model summaries will be presented

1. For the CPRR: the posterior mean, standard deviation, and the following percentiles: 2.5%, 10%, 25%, 50%, 75%, 90%, 97.5%. In addition, the posterior probability that the CPRR is less than 1 and less than 0.90 will be presented.
2. For the log-CPRR: the posterior mean, standard deviation, and the following percentiles: 2.5%, 10%, 25%, 50%, 75%, 90%, 97.5%.
3. For each of the mean rates of decline on the control, in each strata (the α_g), the posterior mean, median, standard deviation, and 95% credible interval will be presented (2.5th to 97.5th percentiles).

 EPAD - 115736	D2.11 Master Statistical Analysis Plan for the EPAD Platform Proof-of-Concept Trial		
	WP2. Statistical/Methodology Engine Room	Version: v2.0 – Final	
	Author(s): [name], [name], [name]	Security: PU	26/36

The primary analysis for an intervention will be considered successful if the posterior probability that the CPRR is less than 0.90 is greater than 0.85. The following analyses will be done on specific subsets of participants:

1. The primary analysis for an intervention will be done on the FAS all controls be based on comparing all randomized participants to the intervention to all participants in the same strata as the specific intervention randomized to a control. This is the dataset called FAS-All controls. We refer to the strata for an intervention as the “signature.”
2. An analysis based on the dataset FAS-Concurrent controls. An analysis based on the dataset FAS-IST controls.
3. An analysis based on the dataset FAS-All controls but only including measurements for $j=0,1,2,\dots$
4. An analysis of different control arms will be conducted in order to check for poolability. This is based on the dataset FAS-Concurrent controls-controls only. All intervention specific controls will be analyzed in a single common run of the BCPM and compared to the control group in the IST: A “treatment effect” CPRR will be fit for each control group (with one intervention chosen to have $CPRR=1$) for the blinded placebo. The posterior mean and 95% credible interval of the ratio of the CPRR between control arms will be presented. If the 95% credible interval for an intervention’s control group does not include 1, this group will be considered to have a different cognitive progression rate.
5. A single instance of the model will be run on the dataset FAS-All controls (each treatment with its own θ_t) with an adjustment for the calendar time of enrolment of the participant in the trial, specific to the strata will be included. The model for the outcome is

$$Y_{ij} = \begin{cases} \gamma_i + \sum_{v=j}^{-1} \alpha_v + \delta_B + \epsilon_{ij} & j = \dots, -2, -1 \\ \gamma_i + \delta_B + \epsilon_{ij} & j = 0 \\ \gamma_i + \exp(\theta_{t_i}) \sum_{v=1}^j \alpha_v + \delta_B + \epsilon_{ij} & j = 1, 2, 3 \dots \end{cases}$$

Where B is an indicator for the “bucket” of time in which a participant was enrolled (specifically the timing of the baseline observation). The indicator B will be based on semi-annual buckets starting and working backwards from the last participant enrolled. The following modelling of the time effects will be used.

$$\delta_B \sim N(\delta_{B-1}, \tau^2), B=S^*, \dots, N_B$$

 EPAD - 115736	D2.11 Master Statistical Analysis Plan for the EPAD Platform Proof-of-Concept Trial		
	WP2. Statistical/Methodology Engine Room	Version: v2.0 – Final	
	Author(s): [name], [name], [name]	Security: PU	27/36

Where S^* is defined as the first 6-month period prior to an intervention starting enrolment in the trial, with the number of 6-month buckets, N_B , a function of the calendar time enrolling the participant. The parameter is modelled as

$$\tau^2 \sim IG(0.01, 0.01).$$

An additional analysis will be conducted where there is a different vector of the δ , where the δ are separate for the clinically +ve and clinically –ve strata.

6. An analysis of the model will be conducted where the CPRR will be separate by each individual strata.
7. The effect of covariates will be examined. As the RBANS values are normalized, the focus will be on models, where the covariates influence the change over time. As the actual covariate will typically be assessed at baseline, this will only use data at and after baseline. Analyses of the BCPM with standardized covariates Z_1, \dots, Z_C will be conducted by the following model

$$Y_{ij} = \begin{cases} \gamma_i + \epsilon_{ij} & j = 0 \\ \gamma_i + \exp\left(\theta_{t_i} + \sum_{c=1}^C \beta_c Z_{ic}\right) \sum_{v=1}^j \alpha_v + \epsilon_{ij} & j = 1, 2, 3 \dots \end{cases}$$

Where the prior distribution of the coefficients for each covariate will be

$$\beta_c \sim N(0, 10^2), c = 1, \dots, C$$

Each continuous covariate will be standardized by the patient-weighted mean and standard deviation for each covariate. Indicator variables will be left as 0/1 variables.

Exploratory analyses will be conducted on an array of covariates.

Subset analyses and additional analyses for each intervention will be specified in the intervention specific SAP.

